
The following assessments will be conducted in the order written post randomisation of clusters:
 
 • Informed consent and assent • Demographics • Medical history • Current/concomitant medications • General physical examination • Vital signs • Hb assessment using Pronto • Anthropometric measurements (height and weight) • Inclusion/exclusion criteria evaluation • Subject Eligibility • 24 hr dietary recall & dietary diversity survey • Parental/LAR training on the completion of the ‘Symptom Check List’ • Dispense blank Parent/LAR Symptom Checklist and Product Compliance Report Forms

 GlaxoSmithKline	Document Name	Clinical Study Protocol 204477		
	Type	Version	Document Identifier	Effective Date
	eldo_clinical_doc	5.0; Most-Recent; Effective; CURRENT	090032d580daa95e	10-Oct-2017 06:16:49
	Reason For Issue	Auto Issue		

Visit 2 - Baseline Visit

The following assessments will be conducted ~~in the order written:~~

- Current/concomitant medications
- Continued eligibility criteria
- Sample collection for urinary Neopterin test & lactulose/mannitol test
- Sample collection for analysis of serum ferritin, sTfR, CRP, AGP, sIgA & nutritional biochemistry (for micronutrients vitamins A, B6, B12, C, D, E, folate, and of the trace elements selenium, zinc, copper, and iron)
- Adverse Event (AE) monitoring

Visit 3, 4, 5, 6, 7, 8, 9, SPWR and Product Administration Visits

The following assessments will be conducted:

- Current/concomitant medications
- Continued eligibility criteria
- Dietary counselling will be administered to all study participants and their parents/LARs.
- Test product will be administered to all study participants in the test group only.
- SPWR visits will be conducted on a weekly basis until End of Study Visit. Parent/LAR symptom checklist & Product Compliance Report Forms will be collected and reviewed.
- Adverse Event (AE) monitoring

Visit 10 - End of Study Visit

The following assessments will be conducted ~~in the order written:~~

- Current/concomitant medication
- General physical examination

 GlaxoSmithKline	Document Name	Clinical Study Protocol 204477		
	Type	Version	Document Identifier	Effective Date
	eldo_clinical_doc	5.0; Most-Recent; Effective; CURRENT	090032d580daa95e	10-Oct-2017 06:16:49
	Reason For Issue	Auto Issue		

- Vital signs
- Anthropometric measurements (height and weight)
- Continued eligibility criteria
- 24 hr dietary recall & dietary diversity survey

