Matching creates comparable groups at baseline and will provide ‘face validity’ regarding balance between treatment arms. Thus matching the clusters prior to random allocation will improve causal effect estimation by improving intergroup homogeneity. Cluster (schools) will be matched for cluster size (in context to the number of children in 7-10 yrs age group), socioeconomic profiles of students, and type of school (government subsidised or private).

After obtaining informed consent and assent, school children aged 7-10 years will be screened to identify eligibility based on the pre-defined inclusion and exclusion criteria. The children will then be allocated to their respective groups, based on the random allocation of the school to which they belong.

Nutritional deficiency and the resulting immunity outcomes can be influenced by dietetic interventions which aim to improve nutritional intakes. These interventions primarily include dietary advice to improve the nutritional quality of the diet and oral nutritional supplement intake.

To test the hypothesis that MN supplementation can improve immunological/clinical outcomes, it is pertinent that the two treatment groups are matched in terms of their background diets. Thus the test group will be administered the test product (fortified malt based food), while both the test and control groups will receive dietary advice (the quality, content and duration of the nutritional counselling will be equivalent for the two groups). Dietary counselling is intended to improve knowledge, attitude and practices as they relate to nutrition and diet, with the overall aim of improving the quality of the diet. Since the impact of parenting on diet is greatest in the early years,

 GlaxoSmithKline	Document Name	Clinical Study Protocol 204477		
	Type	Version	Document Identifier	Effective Date
	eldo_clinical_doc	5.0; Most-Recent; Effective; CURRENT	090032d580daa95e	10-Oct-2017 06:16:49
	Reason For Issue	Auto Issue		

and also, as children spend significant amounts of time with school teachers, both parents and teachers will also be part of the dietary counselling. Dietary counseling will be based on the Dietary Guidelines for Indians, established by the Indian Council of Medical Research (National Institute of Nutrition).

[figure not shown]

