4.1. Inclusion Criteria

A subject will be eligible for inclusion in this study only if all of the following criteria are established:

1. **Consent and Assent**
 Demonstrates understanding of the study and willingness to participate as evidenced by the parent's and/or LAR's voluntary written informed consent as well as written assent by the child and has received a signed and dated copy of the informed consent form as well as the assent form.
2. **Age and Gender**
 Boys and girls aged between 7-10 yrs, inclusive
3. **Compliance**
 Child and parent/LAR understand and are willing, able and likely to comply with all study procedures and restrictions.
4. **General Health**
 Good general and mental health with, in the opinion of the investigator or medically qualified designee:
 - a) No clinically significant and relevant abnormalities in medical history or upon physical examination.
 - b) Absence of any condition that could affect the child's safety or wellbeing or their ability to understand and follow study procedures and requirements.
5. Participants with HAZ of ≥ -3 to ≤ -1 .

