4.2. Exclusion Criteria

1. **Children in Care (CiC):** A child who has been placed under the control or protection of an agency, organisation, institution or entity by the courts, the government or a government body, acting in accordance with powers conferred on them by law or regulation. The definition of a CiC can include a child cared for by foster parents or living in a care home or institution, provided that the arrangement falls within the definition above. The definition of a CiC does not include a child who is adopted or has an appointed legal guardian.

 GlaxoSmithKline	Document Name	Clinical Study Protocol 204477		
	Type	Version	Document Identifier	Effective Date
	eldo_clinical_doc	5.0; Most-Recent; Effective; CURRENT	090032d580daa95e	10-Oct-2017 06:16:49
	Reason For Issue	Auto Issue		

2. Allergy/Intolerance
Known or suspected intolerance or hypersensitivity to the study materials (or closely related compounds) or any of their stated ingredients.
3. Indication that child is likely to move out of geographical range of the study within the period of study intervention and activities, thus hindering the child's compliance to study activities.
4. Clinical Study/Experimental Medication
 - a) Participation in another clinical study or receipt of an investigational drug within 30 days of the screening visit.
 - b) Participation in any nutritional study or didactic nutrition education in the last 6 months of the screening visit.
 - c) Previous participation in this study.
5. Child with severe anaemia (Hemoglobin <8g/dL).
6. Children with history of use of immunosuppressive therapy *e.g.*, oral corticosteroids or chemotherapy in past six months prior to the screening visit.
7. Current or relevant history of any serious, severe or unstable physical or psychiatric illness or any medical disorder that would make the participant unlikely to fully complete the study or any condition that presents undue risk from the test product or procedures, on the discretion of study physician.
8. Recent history [2 months] of serious infections, injuries and/ or surgeries in the opinion of the investigator.
9. Children consuming nutritional supplements and/or health food drinks on a regular basis (≥ 3 times a week) in last 3 months.
10. Personnel
 - a. Child belonging to an employee of the sponsor or the study site or members of their immediate family.
 - b. Sibling of a child already enrolled in the study.

 GlaxoSmithKline	Document Name	Clinical Study Protocol 204477		

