5.9. Product Assignment

Prior to the start of the study, schools within matched pairs will be assigned to test and control group in accordance with the randomisation schedule generated by the Biostatistics Department, GSKCH, using validated internal software.

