5.9.1 Randomisation

A unique screening number will identify each participant screened for study participation. At each school, screening numbers will be assigned in ascending numerical order as each participant's parent/LAR signs their consent form.

This study will follow cluster randomisation where in schools will be termed as clusters and then matched pairs will be formed on the basis of criteria defined in Section 6.1. As schools are determined to be fully eligible and matched pairs are formed, schools within the matched pairs will be randomised according to the randomisation schedule provided to the study centres. Each matched pair will be assigned a randomisation number in ascending numerical order as each matched pair is formed.

Once 60% of participants from any gender have been enrolled within a study group, recruitment into that gender will stop to ensure that there is a maximum 60% of either male or female. Remaining 40% of participants will be recruited from other gender.

The randomisation schedule will be provided by the Biostatistics Department, GSKCH.

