5.9.2 Blinding

This is an open-label study; hence there will be no requirement for blinding of study personnel at site and sponsor/CRO.

The study centre will receive a randomisation schedule to be used by the centre for randomisation of matched-pair clusters. This schedule will have a randomisation number for a matched pair of clusters followed by the study group (test/control) for intervention within clusters.

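### Schools are allocated openly before any child is consented or screened, so who enrols could differ by arm

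*Protocol*

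**What the plan says.** **Order of events.** Under Visit 1, the Protocol Synopsis states: "The following assessments will be conducted in the order written post randomisation of clusters". Consent and assent come first in that list, and eligibility evaluation comes later in it. Section 5.9 says: "Prior to the start of the study, schools within matched pairs will be assigned to test and control group". Section 5.9.1 adds that, once pairs are formed, "schools within the matched pairs will be randomised according to the randomisation schedule provided to the study centres". Neither section asks for a list of children first.

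**Who knows the allocation.** Section 5.9.2 says: "The study centre will receive a randomisation schedule to be used by the centre for randomisation of matched-pair clusters". The same section requires no blinding of site, sponsor or CRO staff. The gender stop in 5.9.1 is tallied by arm during recruitment: "Once 60% of participants from any gender have been enrolled within a study group, recruitment into that gender will stop".

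**Judgement in eligibility.** Inclusion criterion 3 (section 4.1) reads: "Child and parent/LAR understand and are willing, able and likely to comply with all study procedures and restrictions". Exclusion criterion 7 (section 4.2) is left to the study physician's discretion, and criterion 8 reads: "Recent history [2 months] of serious infections, injuries and/ or surgeries in the opinion of the investigator". Age, height-for-age z-score and haemoglobin are objective.

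**Cues to families.** Section 5.3 has product preparation explained during consent. The Schedule of Events dispenses Product Compliance Report Forms at Visit 1, and Appendix 4 shows that these record study-drink doses given at home.

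**Reporting.** SAP Table 14.1.1 fills the screened and not-enrolled rows in the overall column only. SAP Listing 16.2.1.2 gives each screen-failure reason but has no school column.

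**The concern.** In a cluster trial, randomising the schools makes the schools comparable on average. It protects the comparison of children only if recruiting them does not depend on the arm. Here, the staff who invite families and apply the judgement criteria can know whether the school gets the product. A recent serious infection, or a view on whether a family will comply, may bear directly on a primary endpoint of ill days from gastrointestinal and respiratory illness.

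If such decisions differ by arm, the arms can differ in illness risk before any product is given. The direction is open. More illness-prone children joining product schools would work against the product. Healthier or more motivated families joining them would favour it. With four schools, two per arm (SAP 3.3), such an imbalance would also be hard to tell apart from ordinary differences between schools.

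**Working it through.** **1. The plan's numbers reproduce, and the fix leaves them alone.** Inputs from Protocol 9.1: means 7.0 and 6.3, SDs 2.65 and 2.51, two-sided 5% level, 80% power, design effect 1.5, dropout 30%.
- Root-mean-square SD = √((2.65² + 2.51²)/2) = 2.581. For a difference of 0.7 days, the t-test needs 215 per arm.
- 215 × 1.5 = 322.5, so 323 per arm. 323/0.70 = 461.4, so 462 per arm and 924 in total.

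The point concerns the order of events, so these sizes do not change.

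**2. Where selection can occur.** Planned screened 1300, planned enrolled 924 (Protocol 3.3): 1300 − 924 = 376, and 376/1300 = 28.9%. All of these decisions fall after school allocation. The count includes objective failures, so it overstates what judgement could move at screening. It leaves out families who decline before screening, whom the plan does not count.

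**3. Why no size is given.** If a net share f of one arm differs by D expected ill days, the arm difference shifts by f × D. The documents give neither f nor D, nor a sign, so any percentage of the 0.7-day target would only restate whatever was assumed.

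**4. Existing safeguards, one by one.**
- Matching (3.4, 6.1) uses school size, socioeconomic profile and school type. It does not govern which children join.
- The primary model (SAP 4.4.1.2) adjusts for gender and baseline dietary diversity, with school as a random effect. The diversity score is itself measured at screening, after allocation.
- Baseline biomarker and diet summaries (SAP 4.4.2) use the mITT set, which is completers only (SAP 4.1.3), so they mix enrolment selection with dropout. Demographic, haemoglobin and laboratory shift tables in the Safety population are closer to the question.
- Medical history is listed but not tabulated (SAP 4.2.2).

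**5. Which lock is feasible.** Equal schools are assumed: 1300/4 = 325 screened and 924/4 = 231 enrolled per school.
- *Lock after consent.* Screening may follow consent by up to 60 days (Schedule of Events, footnote 2; section 6.2), so the 21-day window from screening to baseline is not compressed.
- *Lock after eligibility sign-off.* Assuming a five-day school week, 21 days hold 15 school days. One is used for the lock, leaving 14. That means 325/14 = 23.2 screenings per school per day, then 231/14 = 16.5 baseline visits. Re-screening is barred (4.3). If a school withdraws before the lock, up to 2 × 325 = 650 screenings could be lost.
- *Lock after Visit 2.* Product starts 1 to 3 days after baseline (Schedule of Events, footnote 4), which forces about 231/3 = 77 baseline visits per school per day.

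The consent-stage lock is the practical choice.

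**The case against.** The strongest reply is that the plan already places allocation after screening. Section 3.4 says: "The children will then be allocated to their respective groups, based on the random allocation of the school to which they belong". Section 3.1 repeats the Visit 1 list without mentioning randomisation, and section 9.3.4 speaks of randomisation at the Baseline Visit. None of these passages says the school's allocation is still closed. The sentence in 3.4 only passes the school's allocation on to the child. The wording in 9.3.4 conflicts with the Synopsis and 5.9 and should be reconciled.

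A second reply is that the trial is open label. That explains why the arm cannot be hidden once treatment starts. It does not require allocation to be known before children are listed, and nor do the reasons given in 3.4 for randomising schools.

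Three objections do stand. First, consent pages are not in the public file, so what control families are told is unknown and the form may already describe both arms. Second, a consent-stage lock leaves later judgement exclusions open, along with continued eligibility and attendance at Visit 2. Third, the remedy may come too late. The protocol took effect in October 2017, while the November 2018 SAP amendment refers to a dry run and SAP 3.3 gives four schools. This suggests that enrolment was over, without proving it.

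**Conclusion.** The point holds as an opportunity for arm-dependent enrolment that the plan neither prevents nor makes visible. It rests on current text in the Synopsis, 5.9, 5.9.1, 5.9.2, 4.1 and 4.2, and on the absence of any provision for concealing allocation at recruitment or listing children beforehand. Size and direction cannot be determined from the documents.

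A reader might infer that enrolment was in fact biased, that it favours the product, or that the bias could equal the planned effect. The documents support none of these. They contain no evidence of differential consent or exclusion, and any size would depend wholly on assumed inputs. A reader might also infer that families know their arm at consent. Section 5.3 makes that possible but does not establish it.

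The change is worth making because a consent-stage lock and by-school reporting are modest steps and the screening data already exist: section 8.2 requires a CRF for every consented and screened child.

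**What to change.** 1. **Lock before opening.** For each matched pair, obtain consent and assent in both schools and lock the consented list before that pair's allocation is opened. Hold the schedule away from the recruiting centre until then. Amend the Synopsis, 5.9, 5.9.1 and 5.9.2, and reconcile 9.3.4. Locking after eligibility sign-off is stronger but optional, given the pace and the possible loss of screenings.
2. **Keep consent arm-neutral.** Use wording that does not reveal the arm, if the form does not already do so. Move the product-preparation instructions (5.3) and the dispensing of Product Compliance Report Forms until after allocation.
3. **Gender limits.** While allocation is concealed, apply the 40–60% limits by school.
4. **SAP reporting.** In Table 14.1.1, give counts by school and arm: screened, ineligible with reasons, eligible, excluded at or not attending Visit 2, and enrolled. Add school to Listing 16.2.1.2. Tabulate the recorded six-month medical history (6.4) by arm and school. Where the counts of children aged 7–10 used for matching are held, report consented children as a share of them. Base the balance check on enrolled or Safety-population summaries, not mITT.

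**Cost.** A protocol amendment, a wait for both schools of a pair before product release, possibly slower recruitment under school-level gender limits, and a few table rows. There are no added visits or participants. Judgement exclusions after allocation and selection at Visit 2 stay exposed and are only monitored through item 4. If enrolment is already complete, only item 4 applies.

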1. INTRODUCTION

The immune system is the body's defence against disease-causing organisms, malfunctioning cells, and foreign particles. Further, resistance to a disease-causing organism or harmful substance is termed "immunity". This ability to offer resistance to a disease can become compromised if nutrition is inadequate.

Substantial research has focused on the role of nutrition and especially on the contribution of vitamins and minerals to the optimum functioning of the immune system. It has been demonstrated that adequate amounts of micronutrients are required for the immune system to function effectively. Available data indicate a role for vitamins A, D, E, B6, B12, folate, and vitamin C, and of the trace elements selenium, zinc, copper, and iron in the proper working of the immune system [Wintergerst *et al* 2007].

Micronutrient deficiencies are widespread in many developing countries in which staple diets are predominately rice-based, intakes of animal-sourced foods are low [Winichagoon P 2002], and regional soil iodine and zinc levels are low [Wanaratna *et al.* 1997 & Alloway BJ 2004]. Children are particularly at risk for such deficiencies as a result of excessive losses of iron, zinc, and/or vitamin A arising from infectious diseases and/or parasitic infections [Filteau SM *et al.* 1994, Koski KG *et al.* 2001 & Egger RJ *et al.* 1990]. Interactions between co-existing deficiencies of vitamin A and iron [Bloem MW 1995 & Bloem MW *et al.* 1989] and vitamin A and zinc [Christian P *et al.* 1998 & Udomkesmalee E *et al.* 1992] may also occur, which may further exacerbate some of these micronutrient deficiency states. Such deficiencies can have far-reaching health consequences, contributing to impairments in growth, neurobehavioral function, and immune competence, and increases in morbidity and mortality [Viteri FE *et al.* 2002]. Macronutrients also have significant role to play in proper functions of immune system. Protein-energy malnutrition is known to cause impaired immunity and increase susceptibility to infection. The most consistent changes in immune competence in PEM are in cell-mediated immunity [McMurray DN *et al.* 1981, Chandra RK 1974]. Depression of cell mediated immunity by PEM could be the result of an absolute or relative deficiency of amino acids for cell multiplication. Moreover, children with PEM are known to have raised levels of plasma cortisol [Soliman AT *et al.* 2000], which can affect the thymic hormones synthesis from thymolymphatic system and result in repeated infections.

There is a wide-spread prevalence of concurrent micronutrient deficiencies, even in apparently normal school age children in India. According to a study by Sivakumar *et al* (2006), a staggering proportion of healthy school children have sub-clinical

 GlaxoSmithKline	Document Name	Clinical Study Protocol 204477		
	Type	Version	Document Identifier	Effective Date
	eldo_clinical_doc	5.0; Most-Recent; Effective; CURRENT	090032d580daa95e	10-Oct-2017 06:16:49
	Reason For Issue	Auto Issue		

deficiencies and/or inadequate micronutrient intakes. Approximately 45-65% of the school children had deficiencies of vitamins B2, B6, and B12. Studies so far have reported anaemia prevalence as high as 42 to 63% in this age group [Gomber *et al.* 2003, Kumar *et al.* 2003, Rao *et al.* 1980, Sethi *et al.* 2003, Sivakumar *et al.* 2006]. Furthermore, dietary surveys indicate that the micronutrient intakes of school age children in India are much below (approximately 30-70%) the recommended levels [Vijayraghavan *et al.* 2000, Sivakumar *et al.* 2006, NNMB 2006]. In a recent randomised, double blind, placebo controlled study conducted by an accredited academic institute in collaboration with GlaxoSmithKline (GSK) [Vaz *et al.* 2011], micronutrient deficiencies of riboflavin and B12 were found to be 88% and 17%, respectively, in apparently healthy school going children (7-10 years).

Micronutrient deficiencies and childhood morbidities have been found to co-exist [Patwari AK 1999]. In India, the most common diseases encountered during childhood are diarrhea and ARIs [Sarkar *et al.* 2013]. Other studies have shown these illnesses to be common across the developing world [Castro *et al.* 2003, Hussain *et al.* 1999]. These illnesses are a threat to the normal growth and development of a child.

Diarrhea and malnutrition often occur in a vicious cycle, with one condition perpetuating the other. It has been found that pre-existing nutritional deficits cause reduced turnover of epithelial cells of the gastrointestinal (GI) lining, resulting in delayed recovery [Patwari AK 1999]. Malnutrition can also compromise the body's defence mechanism thereby making the intestinal lining more vulnerable to colonisation by pathogenic microbes [Patwari AK 1999]. Diarrhea, in turn, causes further loss of nutrients [Bhandari *et al.* 2014, Thacker N. 2007] and hence an exacerbation of the diarrhea and the malnutrition. Several epidemiological studies have demonstrated a negative correlation between diarrhea and physical growth and development [Patwari AK 1999, Torres *et al.* 2000].

Like diarrhea, ARIs are also common illnesses during childhood [Couriel J 2002]. ARIs can further be categorised as upper respiratory tract infections (URTIs) and lower respiratory tract infections (LRTIs). The upper respiratory tract mucosa is the primary site for respiratory virus contact [Bartley J 2010]. URTIs are known to be the most common and include infections like rhinitis (common cold), sinusitis, ear infections, acute pharyngitis, epiglottitis, and laryngitis [Simoes *et al.* Text Ch 25]. Such infections have the potential of leading to severe complications, thereby affecting the growth and development of a child.

 GlaxoSmithKline	Document Name	Clinical Study Protocol 204477		
	Type	Version	Document Identifier	Effective Date
	eldo_clinical_doc	5.0; Most-Recent; Effective; CURRENT	090032d580daa95e	10-Oct-2017 06:16:49
	Reason For Issue	Auto Issue		

Many studies have demonstrated the efficacy or the potential importance of single micronutrients in reducing the incidence, duration and or severity of these common illnesses in children. In a double-blind, randomised, placebo controlled trial conducted in Indian children; it was found that zinc administration, alone, significantly reduced the incidence of acute and prolonged diarrhea. It also reduced the recurrence of diarrhea in these children [Bhandari *et al.* 2014]. In a pooled analysis of randomised controlled trials, zinc administration was demonstrated to expedite recovery from diarrhea [Bhutta *et al.* 2000]. Vitamin D deficiency has been associated with increased incidence and duration of URTIs across ages [Uysalol *et al.* 2013, Cheng-Shiun *et al.* 2013]. In a study conducted in school age children in Bogota, Colombia, Vitamin A deficiency was found to be associated with increased risk of GI and respiratory morbidity [Thornton *et al.* 2014]. The proposed mechanism of action of Vitamin A in reducing respiratory infections is through increased expression of enzymes of the aldehyde dehydrogenase 1A family (ALDH1A) in respiratory tract epithelial cells [Rudraraju *et al.* 2014].

Though these studies demonstrate the importance or the potential importance of micronutrients in supporting the proper functioning of the immune system, in no study has the impact of an MN supplement on these parameters in school age children in India been investigated. Correcting nutritional inadequacy in school age children is critical for optimising child growth and capacity to learn, thereby building a solid foundation for the child's future. Increased morbidity from illnesses that are common in childhood (such as a greater frequency of illnesses, a longer duration of illness, or increased illness severity) is likely to result in increased school absenteeism, thereby negatively impacting total learning days and ability. Therefore, it is of utmost significance to evaluate the effect of MN supplementation in this age group, given that deficiencies are chronic and widely prevalent.

To test the hypothesis that MN supplementation can favorably impact immune functioning relative to no MN supplementation, in the proposed clinical study, children will be randomly allocated to either fortified malt based food (test) group or a control (reference) group⁵. All study participants (irrespective of group allocation), as well as their teachers and their parents or legally acceptable representatives (LARs), also will receive age-specific dietary counseling to optimise nutritional intakes, based on the Dietary Guidelines for Indians, established by the Indian

⁵ To achieve double-blinding, the children in the control group would have to be administered an unfortified calorie free product. However, it was determined that it would be unethical to administer an "empty-calorie" product to growing children, as the consumption of the empty-calorie product may result in the displacement of more nutritious foods in the diet.

 GlaxoSmithKline	Document Name	Clinical Study Protocol 204477		
	Type	Version	Document Identifier	Effective Date
	eldo_clinical_doc	5.0; Most-Recent; Effective; CURRENT	090032d580daa95e	10-Oct-2017 06:16:49
	Reason For Issue	Auto Issue		

Council of Medical Research (National Institute of Nutrition). Thus, the test group will be administered the test product (fortified malt based food) while dietary advice shall be matched in both the test and control groups with respect to the quality, content and duration.

This proposed randomised controlled clinical study is intended to test the hypothesis that a fortified malt based food may improve immunity outcomes in 7-10 year old school age children.

